6.4 Run-in failure criteria

Subjects fulfilling any of the below listed criteria or withdrawing consent prior to randomisation are considered run-in failures and should follow the procedures described in section 8.1.3.1.

- 1. Included in the trial in violation of the inclusion and/or exclusion criteria
- 2. Pregnancy
- 3. Intention of becoming pregnant
- 4. Participation in other clinical trials throughout the trial. Participation is defined as signed informed consent (note; clinical trials do not include non-interventional studies)

6.5 Randomisation criterion

To be randomised, the below randomisation criterion must be answered "Yes".

1. Subjects ability and willingness to adhere to the protocol and satisfactory handling of the pump, including regular changes of the infusion sets and adequate bolus dosing based on the Investigator's judgment

6.6 Criteria for premature discontinuation of trial product or withdrawal from trial

Efforts should be made to ensure Subjects attend and complete all scheduled visits and procedures. There will be a clear distinction between trial product discontinuation and withdrawal from trial by Subject.

6.6.1 Premature discontinuation of trial product

The Subject may be discontinued from trial product at the discretion of the Investigator due to a safety concern.

The Subject must be discontinued from trial product if any of the following applies:

- 1. Included in the trial in violation of the inclusion and/or exclusion criteria and/or randomised in violation of the randomisation criterion
- 2. Pregnancy
- 3. Intention of becoming pregnant
- 4. Participation in other clinical trials throughout the trial. Participation is defined as signed informed consent (note: clinical trials do not include non-interventional studies)

Discontinuations from trial product criteria are applicable from start of the randomisation (Visit 6) throughout the trial until end of treatment (Visit 22).

Subject discontinued from trial product will be followed up as described in Section 8.1.8.1.

 Trial ID: NN1218-3854
 CONFIDENTIAL
 Version: 4.0

 UTN: U1111-1118-2480
 Status: Final

 EudraCT no.: 2010-024054-11
 Page: 37 of 149

6.6.2 Withdrawal from trial

The Subject may withdraw at will at any time. The Subject's request to discontinue from the trial must always be respected.

If the Subject considers withdrawing the Informed Consent the Investigator must underline to the Subject the importance of continuing in the trial despite trial product discontinuation. If the Subject agrees to discontinue trial product but stay in the trial, procedures described in Section 8.1.8.2 should be followed.

If a Subject decides to withdraw consent, the Subject should be encouraged to undergo procedures described in Section 8.1.8.2.

A Subject will be considered "lost to follow up" if the Subject repeatedly fails to attend the scheduled visits and the site is unable to establish contact to the Subject. The following actions must be taken by the site in relation to a Subject who fails to attend the site for a scheduled visit:

- The site must attempt to contact the Subject and to reschedule the missed visit as soon as possible
- The site must re-train the Subject in the importance of maintaining the scheduled visits
- In cases where a Subject is deemed lost to follow up the Investigator must make every effort to regain contact to the Subject (by e.g. telephone calls, e-mails, certified letters or calls to family members or friends as applicable). These contact attempts should be documented in the Subject's medical records. Only if the Subject continues to be unreachable after all contact attempts, the Subject should be considered to have withdrawn from the study with the primary reason being "lost to follow up".

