8.1.8 Withdrawal procedures

8.1.8.1 Premature discontinuation of trial product

If a Subject is discontinued from trial product, as described in Section 6.6.1 after randomisation (Visit 6), the Investigator must ensure that every possible effort is made to undertake the following procedures:

 Trial ID: NN1218-3854
 Version:
 4.0

 UTN: U1111-1118-2480
 Status:
 Final

 EudraCT no.: 2010-024054-11
 Page:
 44 of 149

Subjects discontinuing before or at Visit 12 (Week 6)

- The Subject needs to be called in for a 22A including CGM fitting as soon as possible after awareness of the trial product discontinuation intention. The meal test at Visit 22A should be performed while the Subject still is on trial product according to randomisation unless this is not feasible for safety reasons as judged by the Investigator. (Confirmation that the meal test was performed on trial product will be recorded in the eCRF).
- The Subject will be asked to remain on trial product until completion of Visit 22B (Confirmation that the Subject was on trial product will be recorded in the eCRF)
- The Visit 22B needs to be scheduled 7 days after Visit 22A and serves mainly for transfer of CGM data as specified in Section 2. No additional CGM fitting is needed for these Subjects at this visit.
- The CGM assessment on visit 14 can be omitted for these Subjects

At Visit 22B a treatment discontinuation session must be made in IV/WRS and reason for discontinuation of trial product must be specified in the End of Treatment/Trial form in the eCRF. Final drug accountability must be performed even if the Subject is not able to come to the trial site.

At Visit 22B the Subject should be switched to a suitable marketed product at the discretion of the Investigator. The medication should be recorded on the diabetes treatment history form (please see 8.2.5) in the eCRF.

If the Subject does not wish to continue on trial product until visit 22B (or if continuation on trial product is not possible due to a safety concern as judged by the investigator) then all assessments related to trial product discontinuation must be completed at visit 22A.

Subjects discontinuing after Visit 12 (Week 6)

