- The Subject needs to be called in for a 22A as soon as possible after awareness of the trial product discontinuation intention. The meal test at Visit 22A should be performed while the Subject still is on trial product according to randomisation unless this is not feasible for safety reasons as judged by the Investigator. (Confirmation that the meal test was performed on trial product will be recorded in the eCRF).
- For Subjects discontinuing between Visit 12 and 14 the CGM and 7-7-9 profile assessment on Visit 14 should be performed as planned, since the CGM has been fitted at Visit 12 for these Subjects

Protocol		Date:	04 February 2016	Novo Nordisk
Trial ID: NN1218-3854	COMEIDENELLI	Version:	4.0	

UTN: U1111-1118-2480 CONFIDENTIAL Status: Final Page: 45 of 149

• For Subjects discontinuing between visit 14 and 20 the CGM assessment at visit 22A is not required and will be performed at the key Visit 22.

• For Subjects discontinuing between Visit 20 and 22 the CGM and 7-7-9 profile assessment on Visit 22 should be performed as planned, since the CGM has been fitted at Visit 20 for these Subjects

At Visit 22A a treatment discontinuation session must be made in IV/WRS and reason for discontinuation of trial product must be specified in the End of Treatment/Trial form in the eCRF.

Final drug accountability must be performed even if the Subject is not able to come to the trial site.

At Visit 22A the Subject should be switched to a suitable marketed product at the discretion of the Investigator. The medication should be recorded on the diabetes treatment history form (please see 8.2.5) in the eCRF.

All Subjects prematurely discontinuing the trial product

In addition, all Subjects prematurely discontinued from trial product should after Visit 22A (22B respectively) attend the FU1 and FU2 and continue in parallel with the per-protocol planned key visits: Visit 10, Visit 14, Visit 18 and Visit 22, after randomisation depending on when the Subject discontinues trial product. The following assessments are not applicable for prematurely discontinued Subjects at V22: 4-point SMPG profile, technical complaints, IWRS call.

Contact after premature discontinuation of trial product:

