Subjects that prematurely discontinue trial product will be asked to attend an End of Treatment visit (Visit 22A) and follow-up visit 1 (FU1) 7-12 days after visit 22A and follow-up visit 2 (FU2) 30-35 days after V22A. In parallel they will continue with the per-protocol planned key visits: Visit 10, Visit 14, Visit 18 and Visit 22.

In the following situations, only one visit should take place:

- If V22A is more than 12 weeks after randomisation and before the planned V22, only V22A should be performed instead of V22
- If V14 /V18, and FU2 visit windows overlap according to visit schedule, only V14/V18 should be performed
- If V22 and FU1 visit windows overlap according to visit schedule, only V22 should be performed

Protocol	İ	Date:	04 February 2016	Novo Nordisk
Trial ID: NN1218-3854	CONFIDENTIAL	Version:	4.0	
UTN: U1111-1118-2480	CONFIDENTIAL	Status:	Final	
EudraCT no.: 2010-024054-11		Page:	46 of 149	

If V22 and FU2 visit windows overlap according to visit schedule, only V22 should be performed

Diary records after premature discontinuation of trial product:

The Subject will be handed out premature discontinuation diaries at Visit 22A to record the following:

- Hypoglycaemic episodes. The following information should be recorded:
 - Start date and time of hypoglycaemic episode
 - Time and value of plasma glucose level before treating the episode (if available) and any follow up measurements
 - Whether the episode was symptomatic (Yes/No)
 - Whether the Subject was able to treat him/herself
- Unexplained hyperglycaemic episodes (see section 8.3.3.2)
- Change of Infusion sets and reservoirs (see section 8.3.2.3)
- Meal dates and times (breakfast, lunch, main evening meal, other) in relation to performance of 7-7-9-point profiles and during the CGM period. (see section 8.5.1.4)

Hypoglycaemic and/or unexplained hyperglycaemic episode must be reported in the diary until Visit 22 has been completed.

Withdrawal from trial 8.1.8.2

If a Subject withdraws consent from the trial after randomisation (Visit 6), the Investigator must ensure every possible effort is made to undertake procedures same as those for end of treatment (Visit 22A) including the meal test, as soon as possible after decision of ending trial. The meal test should be performed with trial product according to randomisation unless this is not feasible due to safety reasons as judged by the Investigator.

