18.4 Data handling

If the Subject is discontinued from treatment, withdraws consent, or is lost to follow-up, then the Subject's data will be handled as follows:

- Data already collected and data collected at the EoT visit will be retained by Novo Nordisk, entered into the database and used for the trial report
- Safety events will be reported to Novo Nordisk and regulatory authorities according to local/national requirements

If data is used, it will always be in accordance with local regulations and IRBs/IECs.

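### Section 6.6.2 sends subjects who stop trial product but stay in the trial to the consent-withdrawal procedure, contradicting 8.1.8.1 and putting a small amount of week-16 off-product data at risk

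*Protocol*

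**What the plan says.** Protocol section 6.6 promises two separate pathways: "There will be a clear distinction between trial product discontinuation and withdrawal from trial by Subject". Section 6.6.1 then gives the route for product discontinuation: "Subject discontinued from trial product will be followed up as described in Section 8.1.8.1".

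Section 6.6.2 deals with a subject who is considering withdrawing consent and allows two outcomes. For the subject who stops product and stays: "If the Subject agrees to discontinue trial product but stay in the trial, procedures described in Section 8.1.8.2 should be followed". For the subject who does withdraw: "If a Subject decides to withdraw consent, the Subject should be encouraged to undergo procedures described in Section 8.1.8.2". Both go to the same section.

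Section 8.1.8.2 is written for the second outcome: "If a Subject withdraws consent from the trial after randomisation (Visit 6), the Investigator must ensure every possible effort is made to undertake procedures". These are of the Visit 22A type, including the meal test. After that come V23 and V24 and a recorded reason for withdrawing consent. No key visits are listed.

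Section 8.1.8.1 opens: "If a Subject is discontinued from trial product, as described in Section". Its reference is to 6.6.1 alone. Further down it states a general rule: "In addition, all Subjects prematurely discontinued from trial product should after Visit 22A (22B respectively) attend the FU1 and FU2 and continue in parallel with". Named there as key visits are V10, V14, V18 and V22. It repeats that rule under the contact arrangements after discontinuation.

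**The concern.** The primary estimand is the week-16 difference regardless of treatment discontinuation, analysed on the in-trial period. What separates it from the de jure estimand is the off-product week-16 values of subjects who stop product and stay. Section 6.6.2 describes exactly such subjects and sends them to a procedure without a week-16 visit.

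The opening of 8.1.8.1 makes the conflict worse. It refers only to 6.6.1, which lists an investigator's safety concern and four mandatory criteria. A subject's own wish to stop is not among them. A site could therefore take 6.6.2 as the controlling text for a voluntary stopper.

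Modelling would not repair the gap. Both documents say that the expected number of subjects who stop product but stay is too low to support imputation from that group, so a missing week-16 HbA1c is imputed from the randomised arm as a whole. Neither the protocol amendment nor the SAP's list of changes corrects the cross-reference.

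**Working it through.** **Step A. What each route yields at week 16.** The inputs are the flow chart (HbA1c and 1,5-anhydroglucitol after baseline at V10, V14, V18 and V22; meal test after baseline only at V22, plus Visit 22A), sections 8.1.8.1 and 8.1.8.2, and the reallocation rule in SAP section 2, General considerations. That rule moves Visit 22A data to the next visit at which the assessment is planned. For the primary estimand it discards the moved on-treatment value only when another value falls on the same visit.

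For a subject who stops product by week 12:

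| Endpoint | Route 8.1.8.1 | Route 8.1.8.2 (6.6.2 taken literally) |
|---|---|---|
| HbA1c, 1,5-anhydroglucitol | Measured at V22, off product | 22A value fills an earlier visit; week 16 imputed from own arm |
| 1-hour PPG increment | V22 meal test used; on-product 22A value discarded | 22A value moves to V22, meets no competitor, and is used |
| CGM time in low IG | CGM period ending at V22 | Week 16 missing; model similar to the primary, so imputed from own arm |

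For a subject whose Visit 22A falls more than 12 weeks after randomisation, 8.1.8.1 itself replaces V22 by V22A. HbA1c, 1,5-anhydroglucitol and the meal test from 22A then count as week 16 on either route, so the routes do not differ for those endpoints.

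**Step B. The plan's own power.** With n = 225 per arm and a two-sample noncentral t-test on 448 degrees of freedom, the noncentrality is δ / (SD × √(2/n)).
- Step 1: distance to the margin 0.4 + 0.1 = 0.5, SD 0.8, one-sided 2.5%. Noncentrality 0.5 / (0.8 × 0.0943) = 6.63; power 99.9998% (stated: above 99.9%).
- Step 2: δ = 0.9, SD 3.4, two-sided 5%. Noncentrality 0.9 / (3.4 × 0.0943) = 2.81; power 80.0% (stated: 80.0%).

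**Step C. Subjects affected.** Section 17.1 expects 4% to stop product, half of them leaving the trial.
- Stop product: 0.04 × 450 = 18. Leave: 9. Stop but stay: 18 − 9 = 9, or 2% of 450.
- Nine is an upper bound at this rate. The documents do not say how many stayers would come through 6.6.2, and those stopping after week 12 drop out by Step A. If stops were spread evenly over 16 weeks (my assumption), 9 × 12/16 ≈ 7 would remain.

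**Step D. Effect on the estimates, taking all 9.**
- HbA1c: if the off-product difference is 0 but the imputation carries −0.1, the shift is 0.02 × 0.1 = 0.002 percentage points. If stoppers on the new product are really 0.4 worse than imputed, it is 0.02 × 0.4 = 0.008.
- Step 1 power with 4% missing (432 observed) is still 99.9997%.
- Step 2: if the on-product difference is 0.9 and the off-product difference is 0, using 22A values inflates the estimate by 0.02 × 0.9 = 0.018 mmol/L. In power terms this is 80.0% at 0.9 against 78.4% at 0.9 × 0.98 = 0.882. Subjects who leave the trial are the same on both routes and are left out of this comparison.
- The 4% is a planning figure given as a possible low. At an assumed 10% share of affected subjects, the HbA1c shifts would be 0.010 and 0.040. Step 1 power, even with those values missing and the 0.040 shift, would be 99.99%.

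**The case against.** The strongest defence is that this is a wrong digit in a cross-reference and that the governing rule is clear. Section 8.1.8.1 states twice that all who stop product continue to V22. Section 8.1.8.2 speaks of withdrawn consent, so on its own terms it cannot govern someone who stays. Section 8.1.8.1 also provides for a subject who does not wish to continue product until Visit 22B, and section 11.1 adds a discontinuation trigger (code break) that 6.6.1 does not list. So 6.6.1 is not an exhaustive gate. Much of this stands. A reader might infer that the week-16 data of these subjects are lost; the documents support only a risk, should a site follow 6.6.2 literally.

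Three further inferences go too far.
- That every endpoint becomes missing: the meal test does not, nor do HbA1c and 1,5-anhydroglucitol taken at a 22A after V18, because the SAP moves those values to V22.
- That all retrieved off-product values disappear: late stoppers have no off-product V22 on either route.
- That section 18.4 confirms the loss, because "Data already collected and data collected at the EoT visit will be retained by Novo Nordisk": the sentence does not exclude other data, the abbreviation list defines EoT as end of trial, section 8.3.7 ties it to Visit 24, and section 17 counts post-discontinuation data in the in-trial period.

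The defence does not remove the contradiction. Section 6.6.2 is the text a site would consult while a subject is deciding whether to leave, and it gives an explicit instruction that differs from 8.1.8.1.

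**Conclusion.** The concern holds as an internal contradiction over follow-up, with a small expected effect. Section 6.6.2 conflicts with 6.6, 6.6.1 and 8.1.8.1, and the opening scope of 8.1.8.1 adds to the conflict. Literal compliance would put the off-product week-16 data of earlier stoppers at risk and push the de facto analysis towards the de jure one. In Step 2 this would happen through an on-product meal test standing as the week-16 value.

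At the planned rates the ceiling is about 9 of 450 subjects, with an HbA1c shift of about 0.002 percentage points against a margin of 0.4. The non-inferiority conclusion is not threatened. These figures assume 4% discontinuation with half leaving, all stayers entering through 6.6.2, and no off-product treatment difference. The first assumption could understate the effect; the second overstates it. The correction is more than clerical because the sentence is an operative instruction about which visits take place.

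**What to change.** Reconcile the passages with two wording changes:
- In 6.6.2, change the first cross-reference (stops product, stays in the trial) from 8.1.8.2 to 8.1.8.1. Leave the reference for withdrawn consent as it is.
- In 8.1.8.1, widen the opening scope from 6.6.1 to 6.6.1 or 6.6.2.

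Subjects who stay would then attend the key data-collection visits that the protocol already schedules up to V22. Section 18.4 needs no change. The cost is an amendment to two sentences and a note to sites, with no new visit or assessment. The change concerns data collection only; no rule on stopping or continuing product is proposed.

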6.7 Subject replacement

Subjects who are withdrawn after randomisation (Visit 6) will not be replaced.

6.8 Rationale for trial population

The purpose of this trial is to assess the effect and safety of CSII of faster-acting insulin aspart in the treatment of adult Subjects with T1DM.

The trial population consists of adult Subjects with T1DM who have been treated with CSII for at least six months with the same pump and the same insulin for at least 90 days. This is to reduce pump user-related variability and to increase the likelihood that the Subjects will be able to adhere to the protocol requirements. To avoid potential influence on effect and safety data, at least 50% of the Subjects should consent to not use their own real-time CGM during the trial. Subjects entering the trial using own real-time CGM must switch off the low glucose suspend mode in order to avoid

Protocol		Date:	04 February 2016	Novo Nordisk
Trial ID: NN1218-3854	CONFIDENTIAL	Version:	4.0	
UTN: U1111-1118-2480	CONFIDENTIAL	Status:	Final	

38 of 149

Page:

potential impact of the safety results. This is only applicable for Subjects entering the trial using own real-time CGM integrated with their pump.

EudraCT no.: 2010-024054-11

In diabetes, a likely cause of elevated HbA_{1c} is poor compliance with treatment regimens or atypical course of the disease. Consequently individuals with an HbA_{1c} greater than 9.0% (75 mmol/mol) are not included in the trial. Subjects in good glycaemic control defined as HbA_{1c} < 7.0% may not benefit from further optimisation of glucose control and therefor the lower cut-off value has been chosen. A BMI limit of \leq 35.0 kg/m² is chosen to include as broad a population as possible, while excluding exceedingly obese individuals. The trial protocol requires strict adherence and good Subject compliance.

 Trial ID: NN1218-3854
 Version:
 4.0

 UTN: U1111-1118-2480
 Status:
 Final

 EudraCT no.: 2010-024054-11
 Page:
 39 of 149

7 Milestones

Planned duration of recruitment period, first Subject first visit (FSFV) – last Subject first Visit (LSFV): 26 weeks

End of trial (EoT) is defined as last Subject last visit (LSLV) after 16 weeks of randomised treatment and a 30-day follow-up.

The recruitment period will depend on the screening rate and the screening/run-in failure rate. Recruitment will be closed as soon as the total number of randomised Subjects is possible to reach, taking into account the number of Subjects currently in screening/in the run-in period and the previous screening/run-in failure rate. All Subjects who are in screening/run-in when recruitment closes will be randomised if eligible. All Investigators will be notified immediately when the recruitment period ends and when the limit of 50% of the Subjects wearing their own CGM is met. When the recruitment period ends, no further Subjects may be screened and the interactive voice/web response system (IV/WRS) will be closed for further screening.

Trial registration:

Information of the trial will be disclosed at clinicaltrials.gov and novonordisk-trials.com. According to the Novo Nordisk Code of Conduct for Clinical Trial Disclosure, it will also be disclosed according to other applicable requirements such as those of the International Committee of Medical Journal Editors (ICMJE)²⁴, the Food and Drug Administration Amendment Act (FDAAA)²⁵, European Commission Requirements²⁶⁻²⁸ and other relevant recommendations or regulations. If a Subject requests to be included in the trial via the Novo Nordisk e-mail contact at these web sites, Novo Nordisk may disclose the Investigator's contact details to the Subject. As a result of increasing requirements for transparency, some countries require public disclosure of Investigator names and their affiliations

 Trial ID: NN1218-3854
 CONFIDENTIAL
 Version: 4.0

 UTN: U1111-1118-2480
 Status: Final

 EudraCT no.: 2010-024054-11
 Page: 40 of 149

8 Methods and assessments

